- b) Clinical diagnosis of COPD defined as either a ratio of FEV1 to forced vital capacity < 0.70 or chest CT evidence of emphysema or prior documentation of FEV1/FVC ratio of < 0.7 and clinical evidence of COPD (defined as ≥ 10 pack-year cigarette smoking history, dyspnea, or on bronchodilators)
- c) Medical clearance from healthcare provider to participate in an exercise program
- d) Have access to a computer with Internet connection, a USB port or Bluetooth capability, and Windows XP/Vista/7/8/10 or higher, or Mac OSX 10.5 or higher operating system, or willing to come to VA Medical Center to use study computers
- e) Pedometer with >90% accuracy compared to manual counts on short clinic walk
- f) Competent to provide informed consent
- g) Willingness to make return visits and be available by telephone for duration of study

Exclusion Criteria are:

- a) COPD exacerbation in the previous 1 month
- b) Inability to ambulate with or without assistance
- c) Clinical signs of unstable cardiovascular disease or congestive heart failure
- d) Hypoxemia during 6MWT, i.e. oxygen saturation <85% using supplemental oxygen
- e) Inability to complete questionnaires
- f) Inability to collect at least 5 of 10 days of baseline step counts
- g) Participation in a pulmonary rehabilitation program at time of screening or within the previous 3 months
- h) Participation in another exercise-related research study at time of screening
- i) Plans to participate in an exercise-related research study in the next 12 months
- j) Plans to enroll in a supervised exercise program, such as pulmonary rehabilitation, in the next 6 months
- k) Average baseline step counts of greater than or equal to 10,000 steps per week

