## **Baseline Visit**

### **D.3. Baseline Visit**

When interested subjects are scheduled for the baseline clinic visit, they will be mailed a medical clearance form which will have been signed by their healthcare provider. The signed clearance form must be faxed or submitted to study staff prior to randomization and assignment to a study arm. At the baseline study visit, we will review the participant's medical history and obtain information about demographics, cigarette use, and prior participation in pulmonary rehabilitation. Comorbidities of coronary artery disease, congestive heart failure, diabetes, and other diagnoses that affect the lower limbs (osteoarthritis or degenerative joint disease, hip or knee replacements, rheumatoid arthritis, chronic low back pain, lumbar spine disease, peripheral vascular disease, or peripheral neuropathy) will be noted. We will record medication use and current use of supplemental oxygen. We will also assess history of AEs and related medication use in the previous 12 months since prior AE strongly predicts future AEs (83). Weight and height will be measured for the calculation of body mass index (BMI). Baseline data will characterize the cohort and allow analysis of potential confounders.

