### D.5. Follow-up Clinic Visits and Phone Calls

Follow-up clinic visits will be conducted when subjects are in stable clinical status, where at least 2 weeks have elapsed since the time of their last prednisone or antibiotic course for treatment of a COPD exacerbation. Participants in both arms will be seen in our research clinics at months 3, 6, and 12 (Table 5). At each follow-up visit, study staff will remind participants not to disclose treatment arm. Subjects will be reminded that they should be working to slowly and steadily increase their walking and exercise. Subjects will perform 6MWT, spirometry, and HRQL assessments. All changes in medication or clinical status will be noted, any potential adverse events recorded, and a history of any COPD exacerbations or hospitalizations in the previous 3 months ascertained. We will also assess dyspnea (UCSD Shortness of Breath Questionnaire and MMRC Scale), physical activity (CHAMPS and [name]), and depression (Beck Depression Inventory). Subjects will also complete the following questionnaires: the Barriers to Exercise, Physical Activity Recall, VR-36, MOS Social Support, Bristol's COPD Knowledge, Exercise Self-Efficacy, Epworth Sleepiness Scale, the Brief Pain Inventory (short form, administered at C03, C06 and C12), and the Dietary Questionnaire (only administered at C00 and C12). The intervention subjects will also complete the Intervention Feedback Questionnaire that asks about the subject's experience with the study website and pedometer at the 6-month and 12-month in-clinic study visits. Blood for inflammatory biomarkers will be drawn by venipuncture, packed in a shipping container with an ice pack, and transported to the MAVERIC blood lab for processing and storage. Subjects recruited at VA Boston will be asked to complete DXA scans for body composition and bone mineral density at the 12-month in-clinic visit, and additionally will be asked to complete a body composition measurement using the Omron HBF-306CN. We will exclude any subject with a pacemaker or defibrillator to minimize any potential risks. If subject has previously undergone a DXA scan at the VA Boston Osteoporosis Clinic within 6 months, then the data from the Osteoporosis Clinic may be used and subject does not need to complete a scan specifically for the research study. If a subject does not complete the study-related questionnaires during the in-clinic visit, research staff will contact the subject after study visit by phone to finish the questionnaires over the phone or send the questionnaires home with the subject to be completed and returned in a pre-paid mailer.

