visits and telephone contacts, study staff will assess changes in symptoms, changes in medications, prednisone and antibiotic use, visits to the emergency room, and hospitalizations. At each study visit, participants will be asked to provide the dates and locations of all hospitalizations since the previous visit. Patient report will prompt study staff to request hospital discharge summaries, medication records, chest X-ray reports, CT scan reports, and any additional information. Patient reports will be verified with review of hospitalization and pharmacy records both in and outside VA facilities, whenever possible. [name] major role on the project is to adjudicate the clinical events during the study. He will have no involvement in the day-to-day conduct of the study and will be blinded to subjects' treatment assignment and baseline test results. He will review subject responses and all medical records to determine if an AE or COPD-related hospitalization has occurred. An AE will be clearly defined as "a complex of respiratory symptoms (increased or new onset) of more than one of the following: cough, sputum, wheezing, dyspnea, or chest tightness with a duration of at least 3 days, requiring treatment with antibiotics or systemic steroids" (84). Occurrence of AEs within 14 days of each other will be considered a single AE (85,86). This definition will also be used at the baseline visit for assessment of occurrence of AEs in the year prior to study entry.

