Total number of AEs and COPD-related hospitalizations will be summed over the 12-month study period. Independence of individual AEs will be assured by considering subjects to have experienced a new AE only if they had been off of oral steroids and antibiotics for at least 14 days following the previous AE (86). Given the count data and expected Poisson distribution of number of AEs and hospitalizations, negative binomial regression models (PROC GENMOD) will be used to calculate risk ratios for AE and COPD-related hospitalizations (86). The

multivariate regression model will include number of AEs (or hospitalizations) as the dependent variable, treatment group as the main predictor, as well as study site, number of AEs (or hospitalizations) in the year prior to enrollment, and any unbalanced baseline characteristics.

**Body Composition by DXA Scan:** Body composition and regional fat analysis will be performed at the baseline study visit and the 12-month study visit using standard software available from the manufacturer. For regional fat measurements, the left and right arm cuts pass through the shoulder joints and as close to the body as possible. The leg cuts separate the hands and forearms from the legs, starting with a diagonal cut through the femoral necks. The midline separates the right and left legs. The images obtained from one of our subjects demonstrate the standard cuts that define the arms, legs, and trunk (see figure to the left). These data can be also be used to calculate a waist-hip ratio (i.e., ratio of

central fat to hip fat) in a standardized fashion using the same landmarks as illustrated by the regions defined on the soft-tissue image. The DXA software can be used to define standard waist and hip regions that will allow comparability of these measurements throughout the study. The lower boundary of the central or waist region, which is also referred to as the android region (A, see figure), is the cut through the pelvis at the level of the iliac crests. The upper boundary of the android region extends upwards to 20% of the distance between the pelvis and the top of the shoulders and the lateral boundaries are the arm cuts. The upper boundary of the gynoid region of interest (G, see figure) is the region below the pelvis cut that extends downward from 1.5 times the height of the android region. Lateral boundaries of the gynoid region are the outer leg cuts.

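### The plan gives two different rules for counting a new COPD exacerbation, and the one in the statistics section is not limited to the course that treated the previous exacerbation

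*Combined protocol and SAP*

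**What the plan says.** Two places in the combined protocol and SAP say when a second exacerbation is a new event.

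- **Secondary Outcomes, item d (exacerbation and hospitalization history).** An AE is a symptom complex "requiring treatment with antibiotics or systemic steroids". The merging rule is: "Occurrence of AEs within 14 days of each other will be considered a single AE". There is no drug-free condition. A blinded adjudicator decides from subject responses and medical records whether an AE occurred. The section adds: "This definition will also be used at the baseline visit for assessment of occurrence of AEs in the year prior to study entry".
- **Statistics, analysis of AEs and hospitalizations.** A subject has a new AE "only if they had been off of oral steroids and antibiotics for at least 14 days following the previous AE". AEs are summed over 12 months and analysed by negative binomial regression, with the number of AEs in the year before enrollment as a covariate.

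Three other places bear on this:

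- Section D.5 times follow-up visits so that "at least 2 weeks have elapsed since the time of their last prednisone or antibiotic course for treatment of a COPD exacerbation". That wording is tied to the treating course.
- The closest exclusion criterion is "COPD exacerbation in the previous 1 month". Neither copy of the criteria excludes continuous oral steroid or antibiotic users.
- Section D.3 says "We will record medication use and current use of supplemental oxygen", so continuous users can be identified at baseline.

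**The concern.** The statistics rule names two drug classes but not the reason for prescribing them. Taken at its word, it has two consequences. A subject who stays on an oral steroid or antibiotic is never off treatment for 14 days, so the 12-month count stops at one. For anyone else, a course given for another condition after an AE restarts the clock and can block a genuine later AE.

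Item d does neither. The adjudicator works from one rule and the analysis states another, and nothing says which prevails. Item d is also the definition applied to the prior-year history, so the outcome and its baseline covariate may be counted differently in the same model. At stake are the AE count, its rate ratio and the power stated for it.

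**Working it through.** **1. The two rules on the same cases**

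| Second AE occurs | Item d | Statistics, literal | Statistics, treating course only |
|---|---|---|---|
| Within 14 days of the first | one | one | one |
| More than 14 days after onset of the first, less than 14 days after its treatment ended | two if counted from onset (not stated) | one | one |
| Less than 14 days after a course for another condition, and more than 14 days after the first AE and its course | two | one | two |
| 60 days later, in a continuous user whose added course ended more than 14 days earlier | two | one | two |

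**2. The plan's own figure.** The power section expects 106 AEs in 111 subjects, 106/111 = 0.955 each, and claims 80% power at a rate ratio of 1.70 and 90% at 1.85. With a log rate-ratio test, a 1:1 split and two-sided alpha 0.05 (assumed for AEs), power = Φ(ln RR × √(106/4) − 1.96).

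- RR 1.70: 0.5306 × 5.148 − 1.96 = 0.77, power 78%.
- RR 1.85: 0.6152 × 5.148 − 1.96 = 1.21, power 89%.

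This is a near miss. The macro's formula is not given, so no error is claimed.

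**3. Inside the continuous users, literal rule.** With Poisson counts capped at one, the expected count is 1 − exp(−λ). For mean rate m and a control/WEB ratio of 1.70, λ(WEB) = 2m/2.70 and λ(control) = 1.70 × λ(WEB).

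- m = 0.955: rates 1.203 and 0.707 become 0.700 and 0.507. The ratio is 1.38, and 37% of events are lost.
- m = 1.910 (twice the average): rates 2.405 and 1.415 become 0.910 and 0.757. The ratio is 1.20, and 56% are lost.

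**4. Whole trial.** Let f be the share of continuous users, equal in both arms. The mean per arm is (1 − f) × λ(others) + f × [1 − exp(−λ(continuous))]. The overall uncapped rate is held at 0.955, so in the twofold case the others average 0.955 × (1 − 2f)/(1 − f), which is 0.905 at 5% and 0.849 at 10%. The documents give neither f nor the rate in these users; both are assumptions.

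| f | Rate in continuous users | Control | WEB | Ratio | AEs lost of 106 | Power |
|---|---|---|---|---|---|---|
| 5% | average | 1.1774 | 0.6974 | 1.69 | 2 | 76% |
| 10% | average | 1.1522 | 0.6873 | 1.68 | 4 | 74% |
| 5% | twice | 1.1278 | 0.6745 | 1.67 | 6 | 73% |
| 10% | twice | 1.0530 | 0.6416 | 1.64 | 12 | 67% |

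The power column uses the formula in step 2 with the reduced ratio and count; compare 78% uncapped.

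**5. Scale.** The standard error of the log ratio is about 2/√106 = 0.194 before overdispersion. The shift is ln(1.70/1.688) = 0.007 to ln(1.70/1.641) = 0.035, or 0.04 to 0.18 standard errors.

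**6. Direction (average rate, average share 10%).**

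- 5% control and 15% WEB: 1.1774/0.6773 = 1.74, away from 1.
- 15% control and 5% WEB: 1.1271/0.6974 = 1.62, toward 1.
- 10% in both arms, no effect in continuous users: uncapped (0.9 × 1.2025 + 0.1 × 0.955)/(0.9 × 0.7074 + 0.1 × 0.955) = 1.61. Capped, with 1 − exp(−0.955) = 0.615 replacing 0.955, it is 1.64, away from 1.

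**The case against.** The best defence is that the statistics clause means the treating course. It follows a reference to the previous AE, and an AE is by definition an event that requires these drugs. Section D.5 spells out that meaning for visit timing. This reading is available and may be what the sponsor intended. But the sentence does not say so, and the narrower wording shows that the limit could have been written in. Even on the narrow reading the two rules measure different intervals, one between AEs and the other since treatment ended.

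A reader might go further and infer that continuous users can never have a second AE counted. The documents do not support that. Item d would count a second AE more than 14 days later whatever the subject takes, and nothing says the statistics clause overrides it.

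A reader might also infer that the AE ratio is necessarily pulled toward 1. Step 6 shows that this needs similar shares and a similar effect across arms.

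Three further limits stand. No document gives AE rates by maintenance therapy, so a higher rate in these users is an assumption. The 106 expected AEs come from preliminary data whose counting rule is not stated, so some loss may already be included. The drug-free clause is written for AEs, not hospitalizations, and the primary 6MWT analysis is untouched.

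**Conclusion.** The concern holds as a conflict between two counting rules, one of which, read literally, drops genuine exacerbations in continuous users and after unrelated courses. Because item d also defines the prior-year history, outcome and covariate may rest on different definitions.

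The numerical effect is probably small: a true 1.70 reads about 1.69-1.64, with 2 to 12 of 106 AEs lost. This assumes that 5-10% of both arms are continuous users, with one to two times the average AE rate, a common true ratio and Poisson counts. The larger subgroup figures (1.20, and 56% lost) apply only within that hypothetical group at twice the average rate. The direction cannot be fixed from the documents. Blocking by courses for other conditions was not quantified. The point is worth settling before AEs are counted, because the rule can change the result and the correction is cheap.

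**What to change.** Reconcile item d of Secondary Outcomes and the AE paragraph of the statistics section into one event-counting rule:

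- A new AE counts when at least 14 days have passed since the end of the antibiotic or steroid course prescribed for the previous AE.
- Unchanged maintenance therapy, and courses for other conditions, do not block a new AE.
- The same rule applies to follow-up counts and to the prior-year history used as a covariate.
- The blinded adjudicator receives the same wording.

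The cost is a sentence or two in each place and in the adjudication instructions. Baseline medication is already recorded, and the adjudicator already reviews medical records. The downside is that the adjudicator must judge why a course was prescribed, which may be harder for prior-year events. The change concerns event counting only, not patient care.

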In the secondary analyses of daily step count, we will compare the number of no-wear days and the number of participants nonadherent with monitoring between arms. Nonadherence with step-count monitoring, which is different from treatment fidelity, will not affect the primary aim of the study to examine the efficacy of WEB to increase exercise capacity, as indicated by 6MWT distance.

**f. Assessment of Body Composition and Bone Mineral Density (VABoston site only):** We will use a 5th generation GE Healthcare iDXA dual x-ray absorptiometry (DXA) scanner with enCore configuration version 12.3 to determine BMD, to assess total body composition, and

perform regional fat and lean mass analyses. As part of the study, participants will have DXA scans performed at baseline and approximately 12 months from baseline. For BMD assessment, scanning will be performed at the hip, the distal radius, and the spine. Regions with evidence of heterotopic ossification will be excluded from analyses since this will interfere with the accurate determination of BMD. Additionally, subjects will be asked to complete a body fat reading using the Omron Fat Loss Monitor (model HBF-306CN) for comparison of body fat measurement with the DXA scan, at baseline and approximately 12 months from the baseline study visit. We will exclude any subject who is pregnant or who has a pacemaker or defibrillator to minimize any potential risks.

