**Power Calculation:** This study is powered on our pre-specified primary outcome of 6MWT distance. Our main comparison is 6MWT distance at 6 months between the WEB intervention and control arms. Our power analysis is based on a widely accepted minimum clinically meaningful change in 6MWT distance of 54 meters and the published standard deviation for 6MWT distance of 80-120 meters (90). Our data in a similar Veteran population showed a standard deviation of 102 meters for 6MWT distance. We use a standard deviation of 100 meters in our power calculation. Using the sample size formula for the comparison of the means of 2 independent samples, we calculate that 55 evaluable subjects in each arm at 6 months will allow

[figure not shown]

detection of a difference of at least 54 meters between the WEB and usual care arms with a power of 80% and  $\alpha=0.05$ . We anticipate a maximal drop-out of 40% at 6 months. In order to have 111 evaluable subjects at 6 months, we plan to enroll a total of 185 subjects.

**Secondary Aims:** To estimate the effect of the WEB intervention on (a) HRQL, as measured by the St. George's Respiratory Questionnaire (SGRQ), (b) dyspnea, (c) CRP and IL-6, (d) risk of AEs and COPD-related hospitalizations, (e) engagement in PA as measured by daily step count, (f) body composition and bone mineral density, and (g) pain.

Our statistical analysis plan for the secondary outcomes is similar to that for the primary outcome. We will use 2-way factor analysis or analysis of variance (ANOVA) to assess the effect of intervention versus control on SGRQ-TS, dyspnea score, CRP and IL-6, and daily step count. We will analyze absolute values of the secondary outcomes at baseline and 6 months. Two-way ANOVA will allow us to examine the effect of our intervention, and additionally allow us to assess the interaction between treatment and time (treatment-time) on the secondary outcomes. We will use a mixed model (PROC MIXED in SAS) to perform the 2-way ANOVA. Models will have SGRQ-TS, dyspnea score, CRP and IL-6, or daily step count as the dependent variable, and treatment, time, and treatment-time as independent variables. Models will also include study site and any unbalanced baseline characteristics as covariates.

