The waist to hip fat ratio, or android to gynoid ratio, is the percent fat in the android region divided by the percent fat in the gynoid region. Percent fat mass in each region is reported as the total of the percent fat in the right and left sides. The precision of regional fat measurements is +/-1%.

Subjects will be asked to complete a body composition measurement using the Omron Fat Loss Monitor (model HBF-306CN) in order to compare body fat measurements with the DXA. Since DXA is the gold standard, the Omron Fat Loss Monitor is being examined as a cost-effective and less invasive alternative method to measure body fat composition. The monitor has been approved for use in the general population except in individuals who are pregnant or who have implanted medical devices such as pacemakers or defibrillators; we will therefore exclude any subject who is pregnant or who has a pacemaker or defibrillator to minimize any potential risks.

**Anticipated Results:** We anticipate that subjects in the intervention group will have better HRQL, less dyspnea, lower CRP and IL-6 levels, higher daily step count, lower adiposity, higher bone mineral density and lower risk of AEs and COPD-related hospitalizations compared to subjects in the control group at 6 months.

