### **Additional Analyses**

Additional analyses will be conducted with repeated measures ANOVA using all time points--baseline, 3, 6, and 12 months assessments of 6MWT distance--to explore the effect of the interaction between treatment and time (treatment\*time), as well as the between-subject group treatment effect (intervention versus control) and the within-subject effect (repeated over time) on 6MWT distance. We will use a mixed model (PROC MIXED in SAS) to perform the repeated measures ANOVA. We will examine both compound symmetry and AR(1) correlation structures. Models will have 6MWT distance at each time point as the dependent variable, and treatment,

time, and treatment-time as independent variables. Models will also have study site and any unbalanced baseline subject characteristics as covariates. Similarly, additional analyses will be conducted with repeated measures ANOVA using all time points--baseline, 3, 6, 9, and 12 months assessments of the secondary outcomes--to explore the effect of the interaction between treatment and time (treatment-time), as well as the between-subject group treatment effect (intervention versus control) and the within-subject effect (repeated over time) on SGRQ-TS, dyspnea score, CRP and IL-6 levels, and daily step count. We will use a mixed model (PROC MIXED in SAS) to perform the repeated measures ANOVA. Models will have the secondary outcome at each time point as the dependent variable, and treatment, time, and treatment-time as independent variables. Models will also have study site and any unbalanced baseline subject characteristics as covariates.

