**Analytic Approach:** For neuroimaging, all analyses will be performed with complementary advanced imaging procedures for brain network mapping, including seed-based and independent component analysis procedures, to assure the robustness of the findings. We will correlate neuroimaging data with clinical data obtained at baseline in the main study, including demographics, dyspnea, chronic pain assessments, and daily step count as the measure of PA. We will perform secondary analyses to examine the potential influence of PA and clinical characteristics that may contribute to the findings. We will be somewhat exploratory in our approach in this pilot project, while also being mindful of statistical considerations. Our main image analyses will use robust and careful seed based DMN mapping procedures. Analyses will account for known contributors to the fcMRI signal including motion, respiration and cardiac signals. Neuroimaging data will be processed using a combination of FreeSurfer. AFNI. and FSL. based primarily on the FSL processing stream. Surface models will be reconstructed from anatomical images using FreeSurfer. Resting state fcMRI scans for each subject will be

processed using a standard stream (motion correction, time shifting, concatenation of scans, motion regressed from time series, regression of the global mean and the average time courses from the white matter and the ventricles, band pass filtering between 0.01 and 0.1 Hz). Time points, runs, and sessions with excessive motion will be excluded (0.5 mm/TR; 20 TRs/run; 30 TRs/session). Data will be sampled to and smoothed on the surface, and each brain will be warped to a surface-based template (fsaverage). Seed regions will be derived from surface-based parcellations of the cortex providing more robust anatomical representation for each participant. The vertex-wise partial correlation to the seed will allow further group-level analyses. We will focus on the DMN, but explore other networks including pain networks. We will also explore resting state functional connectivity associated with the anticipatory symptom scenarios.

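### Body-composition and bone-density differences are predicted at 6 months, but DXA is done only at baseline and month 12 in Boston; no between-arm DXA model is given, and the 0.55 SD precision does not apply to that subset

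*Combined protocol and SAP*

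**What the plan says.** In the Statistics (power analysis) section, the secondary aims include "f) body composition and bone mineral density, and (g) pain". The analysis paragraph that follows states: "We will analyze absolute values of the secondary outcomes at baseline and 6 months". It then describes a mixed model with treatment, time, treatment-by-time, study site and unbalanced baseline characteristics, and names the outcomes: "Models will have SGRQ-TS, dyspnea score, CRP and IL-6, or daily step count as the dependent variable".

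The Anticipated Results paragraph for the secondary aims predicts "higher daily step count, lower adiposity, higher bone mineral density" among its benefits and closes with "higher bone mineral density and lower risk of AEs and COPD-related hospitalizations compared to subjects in the control group at 6 months".

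On measurement, item f of the Secondary Outcomes in D.6 says "participants will have DXA scans performed at baseline and approximately 12 months from baseline", under a heading that limits it to the Boston site. The design text in Work Proposed (b), section D.5, Table 5 with its footnotes, and the DXA paragraph of the Statistics section all give the same two visits. Bioimpedance is taken at those visits and only if the DXA scan is completed.

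The Power Calculations paragraph for the secondary aims says that 111 evaluable subjects at 6 months also suffice for the secondary outcomes, with a detectable effect of 0.55 SD at 80% power.

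**The concern.** The stated hypothesis needs a month-6 value of fat mass and bone density in each arm, and the schedule produces none. The only time-point rule that could cover a secondary aim without its own model points to a visit without scans. The text that does concern DXA in the Statistics section covers scan regions, the android-to-gynoid ratio and the comparison of the handheld device with DXA. It sets out no comparison of treatment arms.

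Two things are at stake. First, analysts would have to choose the form of the treatment comparison for this aim themselves: change or follow-up value, which covariates, which participants. If they do so after seeing data, the result cannot be reported as pre-specified. Second, a reader of the power section would take 0.55 SD as the precision for every secondary outcome, although the DXA outcomes come from one of two sites and from a visit six months later than the one at which the 111 are counted.

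**Working it through.** **1. Measurement times against hypothesis times**

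| Outcome | Time in Anticipated Results | Scheduled measurement | Between-arm model given |
|---|---|---|---|
| Adiposity, BMD (DXA) | 6 months | Baseline and month 12, Boston only | None |
| Bioimpedance body fat | not named separately | Same visits, only if DXA is done | None |
| Exacerbations, hospitalizations | 6 months | Counted over 12 months | Negative binomial, full covariate list |
| SGRQ, dyspnea, CRP, IL-6, steps | 6 months | Include baseline and month 6 | Mixed model, baseline and month 6 |

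Scheduled DXA measurements at month 6: 0. A recent Osteoporosis Clinic scan may replace a study scan, so an occasional scan could fall near month 6, but this cannot supply a randomized 6-month comparison.

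The exploratory all-visit models under Additional Analyses name the same outcomes as the main secondary model and no DXA outcome.

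**2. The plan's own sample size, reproduced**

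Inputs from Power Calculation: difference 54 m, SD 100 m, power 80%, alpha 0.05 (taken as two-sided).

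n per arm = 2 × (1.96 + 0.8416)² × 100² / 54² = 53.8, so 54. The t-test version gives 54.8, so 55, as stated. With 40% drop-out, 185 × 0.60 = 111.

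Detectable effect with 111 evaluable (55.5 per arm): (1.96 + 0.8416) × √(2/55.5) = 0.53 SD, or 0.54 SD by t-test. The plan's 0.55 SD is consistent with this, slightly rounded up. One-sided alpha would give 43 per arm and does not reproduce the plan.

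**3. The same calculation for the DXA subset**

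The documents do not give Boston's share. Work Proposed (a) expects the same rate, 3 to 4 subjects per month, at each site, so half is a reasonable working assumption: 111 / 2 = 55.5 in Boston, about 27 to 28 per arm. This also assumes that everyone evaluable at month 6 is scanned at month 12.

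Two-sample t-test, two-sided alpha 0.05, 80% power, no baseline adjustment:

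| Per arm | Detectable difference |
|---|---|
| 55.5 (both sites, month 6) | 0.54 SD |
| 28 | 0.76 SD |
| 27 | 0.78 SD |
| 20 | 0.91 SD |

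With 27 to 28 per arm, power at 0.55 SD is about 51 to 52%.

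**4. Range over the assumptions**

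Let 40 to 70% of the 185 be in Boston and 50 to 80% of those have a month-12 scan.

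- Low end: 185 × 0.40 × 0.50 = 37 subjects, detectable difference 0.95 SD.
- High end: 185 × 0.70 × 0.80 = 103.6 subjects, detectable difference 0.56 SD.

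The stated 0.55 SD is approached only at the top of this range.

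**The case against.** The strongest reply is that the time point is not in real doubt. Every scheduling passage, including the DXA paragraph inside the Statistics section, gives baseline and month 12, and there is only one follow-up scan to analyse. The phrase about 6 months closes a long list of expected results and is not an analysis instruction. This stands. A reader might infer that the aim is lost, but the documents do not support that: the baseline-to-12-month data will exist.

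A reader might also infer that the plan fits the 6-month mixed model, with its site term, to DXA. It does not say so, because the outcomes named for that model exclude DXA. Only the general sentence on secondary outcomes reaches it. But if that sentence was not meant for DXA, the aim has no comparison of arms at all, so a correction is needed on either reading.

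A third inference would be that the exacerbation analysis is undefined. It is not: the window, model and covariates are set over 12 months, and its power is computed on 12-month follow-up. Only the closing phrase of the sentence disagrees.

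A reader might also object to month 9 in the exploratory models, "using all time points--baseline, 3, 6, 9, and 12 months assessments of the secondary outcomes--to explore", since no blood is drawn then. That list covers several outcomes, some of which are collected at month 9, and a mixed model for CRP or IL-6 simply uses the visits that exist. It is not a defect.

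On size, the detectable differences above are unadjusted. Adjusting for the baseline scan multiplies them by √(1 − r²), where r is the baseline-to-month-12 correlation. Purely as illustration, r = 0.7 gives 0.76 to 0.78 × 0.714, about 0.54 to 0.56 SD; r = 0.9 gives 0.76 to 0.78 × 0.436, about 0.33 to 0.34 SD. The documents give no r, so the gain cannot be fixed. This limits how pessimistic one should be, but it does not rescue the statement in the plan, which rests on 111 subjects and makes no baseline adjustment.

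Finally, the plan converts 0.55 SD into units only for SGRQ, CRP and IL-6. That is so, but the sentence introducing it speaks of the secondary outcomes without exception.

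**Conclusion.** The point holds as a time-point error, a missing model and an inapplicable precision statement for one secondary aim. The 6-month contrast in body composition and bone density has no data behind it, and no between-arm DXA analysis is specified. The 0.55 SD figure does not describe the Boston subset: an unadjusted comparison detects about 0.76 to 0.78 SD if half of the 111 are in Boston and all are scanned at month 12, and about 0.91 SD with 20 per arm. Those figures depend on the Boston share and on month-12 completion, neither of which the documents give. Baseline adjustment would reduce them by an unknown amount. The mismatch in the exacerbation wording is a matter of consistency only. The primary outcome, its analysis and the sample size are not touched.

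**What to change.** - **Anticipated Results (secondary aims):** state the adiposity and bone-density hypotheses at 12 months in Boston participants. Give the exacerbation and hospitalization hypothesis over the 12-month window that the analysis and power paragraphs already use.
- **Secondary Aims analysis:** add a between-arm comparison of month-12 DXA values, adjusted for the baseline DXA value, in Boston participants and without the study-site term, which a one-site subset cannot estimate. Applying the plan's treatment-by-time model at baseline and month 12 would also give a treatment contrast; the baseline-adjusted form is preferred here because it uses the baseline scan directly. Either way, one form should be named in advance.
- **Power Calculations (secondary aims):** limit the 0.55 SD statement to outcomes measured at both sites, and give DXA precision separately with the assumed Boston share and month-12 scan completion.

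The cost is a change of wording, with no new visits or scans. The one drawback is that the stated precision for DXA becomes less favourable.
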